### Guidelines for Preparing a Research Protocol

---

#### Instructions:

- You do not need to complete this document if you are submitting an *Application for Exemption* or *Application for a Chart Review*.
- Do not use this template if:
  - Your study involves an FDA regulated product. In this case, use the *Clinical Trial Protocol Template*.
  - Your study has a protocol from a sponsor or cooperative group. In this case, use the *Protocol Plus*.
  - Your study is a registry or repository for data and/or samples. In this case, use *Protocol Template – Registry Studies*.
- If a section of this protocol is not applicable, please indicate such.
- Do not delete any of the text contained within this document.
- Please make sure to keep an electronic copy of this document. You will need to use it, if you make modifications in the future.
- Start by entering study information into the table above, according to these rules:
  - Protocol Title: Include the full protocol title as listed on the application.
  - Investigator: include the principal investigator's name as listed on the application form
  - Date Revised: Indicate the date at which the protocol was last revised
  - IRB Number: Indicate the assigned IRB number, when known. At initial submission, this row will be left blank.
- Once the table information is entered, proceed to page 2 and complete the rest of the form.

↓ Continue to next page to begin entering information about this study ↓

## 1. PREVIOUS STUDY HISTORY

Has this study ever been reviewed and rejected/disapproved by another IRB prior to submission to this IRB?

No  Yes – if yes, please explain: ]

## 2. BRIEF SUMMARY OF RESEARCH

- *The summary should be written in language intelligible to a moderately educated, non-scientific layperson.*
- *It should contain a clear statement of the rationale and hypothesis of your study, a concise description of the methodology, with an emphasis on what will happen to the subjects, and a discussion of the results.*
- *This section should be ½ page*

The purpose of this pilot study is to determine the feasibility of using N-of-1 methods in a virtual research study with Northwell employees aged 45-75 years old to increase low-intensity walking by 2,000 steps per day/5 days per week using four behavior change techniques, provided in random order, and shown to have been effective in changing physical activity. This pilot will help determine if a Personalized Trial design can have widespread use in future research and clinical practice.

In preliminary phases, participants, via secure surveys delivered electronically and/or via interactive Microsoft Teams meeting(s) for focus groups and/or 1:1 interviews, will finalize the content and design features used to deliver the study messaging.

Up to 60 participants will provide feedback on key aspects of study design, including BCT description, materials and electronic delivery methods, such as text messaging and email receipt. Focus group techniques, interviews and/or surveys may be used to elicit feedback concerning the clarity of instructions and convenience of messaging. At least 10 of these participants will engage with study materials and procedures as “mock participants,” interacting remotely from their home or office, and providing feedback about the ease and acceptability of study procedures to further refine study materials and procedures. In the final, intervention phase of the study, up to 60 participants will be randomized to the 10 week personalized trial assessing the impact of 4 BCTs assigned in random order on their walking behavior.

Participants will be sent a Fitbit physical activity monitor that will track the number of steps taken per day. Depending upon the BCT assigned, the participant will

receive up to four text message prompts per day. They will complete a measure of self-efficacy (i.e. confidence in their ability to walk without stopping) and a ‘satisfaction with BCT’ survey once every two weeks. At the end of their trial, participants will receive a satisfaction survey and a summary of their observed data to help them learn more about their responses to the four behavioral change techniques and to inform investigators as to the feasibility of N-of-1 study design for future research and clinical applications.

### 3. INTRODUCTION/BACKGROUND MATERIAL/PRELIMINARY STUDIES AND SIGNIFICANCE

- *Describe and provide the results of previous work by yourself or others, including animal studies, laboratory studies, pilot studies, pre-clinical and/or clinical studies involving the compound or device to be studied.*
- *Include information as to why you are conducting the study and how the study differs from what has been previously researched, including what the knowledge gaps are.*
- *Describe the importance of the knowledge expected to result*

This study is a pilot project under the umbrella of the NIH-funded grant “Roybal Center for Personalized Trials: Physical Activity Promotion to Foster Healthy Aging.” (Northwell IRB 20-0355) which is funded to test exercise promotion use cases appropriate for N-of-1 methodology and evaluate them for acceptability and scalability.

The overarching objective of our parent grant is to develop, test, and implement an innovative technology platform for conducting personalized trials that transforms precision therapeutics for exercise promotion in older adults. Right now, clinicians are engaging in clinical encounters in which they are trying to determine the best therapy for individual patients. Clinicians rely on the best available evidence (e.g., results from parallel group, phase III randomized clinical trials; RCTs) for recommending therapies to a patient. Yet, conventional, between-group RCTs only provide estimates of the effect of therapies on the hypothetical ‘average’ patient in those trials. Individual patients, however, often respond differently than the hypothetical average patient in the phase III RCTs, and thus, heterogeneity of therapy response plagues clinical decisions made for an individual patient every day.

Personalized trial designs provide a method for tailoring interventions to individual patients and then evaluating the efficacy of these interventions. In many ways, **Personalized Trials are the foundational design for a truly patient-centered approach by serving as a clinical decision tool for patients.** Historically, in introducing evidence-based medicine, Guyatt and others have described Personalized Trials as the pinnacle of the evidence-based design pyramid. Personalized Trials are specifically designed to help patients and their clinicians make healthcare decisions that are informed by high-integrity, evidence-based information uniquely relevant to the outcomes and values important to them.

Yet, clinicians and patients do not routinely engage in this type of scientific endeavor because they lack the tools and resources to implement efficiently. In post-mortem assessments as to why Personalized Trials had yet to become commonly employed, proponents concluded that they were insufficiently appealing to patients or clinicians to justify the cost and effort needed to design and implement them. Specifically, Personalized Trial design specifications had mostly been driven by clinicians or researchers with little input from patients.

### **Rationale for Selecting Four Behavioral Change Interventions as a Personalized Trial for Increasing Low Intensity Physical Activity in Older Adults**

Guidelines and recommendations focus on increasing physical activity for older adults, but adherence to recommendations remains low. This is despite the fact that any increase in physical activity is associated with benefit (LIFE trial). Increasing physical activity meets all of our criteria for selection as a use case as outlined in our umbrella grant: it has high public health burden, high heterogeneity of therapy response, and is high priority for a Personalized Trial approach as determined by previously interviewed clinicians and patients. This instance will adapt our personalized, virtual trial platform to testing the efficacy of four behavioral change techniques consistent with theory (Lally & Gardner, 2013) and randomized clinical trials (Lally et al., 2010). This pilot test will enable us to expand our personalized, virtual trial platform of behavioral interventions. Of note, it is possible that personalized trials of behavioral change techniques could eventually be conducted at the direct-to-consumer level.

Without development of innovative platforms for conducting Personalized Trials, with within-participant randomization to eligible wellness management options, patients and clinicians cannot obtain the objective data they need to empirically choose the optimal precise therapy. Scientists may be able to use Personalized trials to better understand the uniqueness of responders versus non-responders. Should this study demonstrate scalable implementation, acceptability and satisfaction with this methodology amongst participants, it will be a critical step in broadening the application and utilization of this methodology to promote wellness behaviors.

#### **4. OBJECTIVE(S)/SPECIFIC AIMS AND HYPOTHESES**

- *A concise statement of the goal(s) of the current study.*
- *The rationale for and specific objectives of the study.*
- *The goals and the hypothesis to be tested should be stated.*

The specific aims of the study include:

-Eliciting and incorporating participant feedback in the development of required content and study procedures for implementation of a personalized, virtual

interventional trial to enhance low-intensity walking using behavioral change techniques

- Determine the feasibility of conducting a virtual, randomized control trial using participant selected behavioral change techniques
- Examine the novel individual-level heterogeneity of treatment effect made possible by the crossover, personalized trial design, and pool results across patients to efficiently estimate the overall efficacy of the four behavioral change techniques in increasing low-intensity walking by 2,000 steps, 5 days per week.
- Assess the relationship between individual behavior change techniques and walking self-efficacy.
- Elicit participant attitudes and opinions toward using Personalized Trials to help inform their personal wellness strategy

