## 8. NUMBER OF SUBJECTS

- *Indicate the total number of subjects to be accrued locally. If applicable, distinguish between the number of subjects who are expected to be pre-screened, enrolled (consent obtained), randomized and complete the research procedures.*
- *If your study includes different cohorts, include the total number of subjects in each cohort.*
- *If this is multisite study, include total number of subjects across all sites.*

We expect to pre-screen and enroll up to 180 potential participants in this study. Up to 60 participants will be recruited across the four preliminary (brief duration) phases. Up to 60 participants will be randomized to the 10 week personalized trial, first undergoing a 2 week baseline monitoring of their walking behavior, followed by 8 weeks of monitoring their walking in response to each of the four behavioral change techniques (2 weeks per technique).

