#### Intervention Delivery

This pilot study will use text messages to deliver four behavioral change techniques identified in Michie et al.’s (2011) paper which identified those BCTs associated with influencing change in physical activity behavior. These BCTs were updated to align with current BCT definitions using Michie et al.’s (2013) Taxonomy of Behavioral Change Techniques. A list of BCTs is provided as an appendix to this protocol. Participants will also receive **bi-weekly surveys** to assess their satisfaction with the given BCT and walking self-efficacy. BCTs will be provided to participants in a randomized crossover design with each BCT delivered individually in one of four 2-week blocks. The order in which participants receive BCTs will be randomized with the randomization order determined by the study

statistician. Prior to BCT delivery (i.e. every two weeks) participants will be sent information/BCT descriptions the day before they start their new BCT so that they understand the differences between the four BCTs for their personalized trial. For instance, BCT descriptions may include:

BCT Name	Definition	Sample Text Message Prompt
Goal Setting Behavior	Set or agree on a goal defined in terms of behavior to be achieved	Set the goal of being more active today. Record your goal
Action Planning	Prompt detailed planning of performance of behavior (must include a setting frequency, duration, and intensity)	“It’s Tuesday. Walk 2,000 steps from 10am -11am this morning.”
Self-Monitoring of Behavior	Establish a method for person to monitor and record their number of active periods based on their Fitbit	“It’s time to check your FitBit dashboard and view how active you have been today.”
Feedback on Behavior	Monitor and provide informative or evaluative feedback on performance of the behavior (e.g. form, frequency, duration, intensity)	“You met your goal yesterday. You walked 2,000 steps more than baseline.”

Participants may receive additional text messages to those outlined above with important reminders to sync their data as needed.

Upon completion, participants in the personalized trials phase will receive an individual report that demonstrates their walking responses in relation to their assigned BCTs and a satisfaction survey to obtain feedback about their personalized trials experience.

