## 12. STATISTICAL ANALYSIS

- *Describe how your data will be used to test the hypotheses.*
- *State clearly what variables will be tested and what statistical tests will be used.*
- *Include sample size calculations.*
- *If this is a pilot study, state which variables will be examined for hypothesis generation in later studies.*

The sample size of 60 participants for testing the Personalized Trial was chosen to have a sufficient number of participants to obtain a preliminary assessment of the feasibility of Personalized Trials of the four behavioral change techniques as

compared to baseline. The numbers of prompts and reports were based on expert recommendations and estimations about maximal duration of the trial to maintain patient engagement. Data will be reported transparently so that individual level heterogeneity can be assessed.

Means and standard deviations of step scores for baseline versus behavioral change strategy treatment period will be visualized using a column graph. The statistical significance of differences will be adjusted for time interval. The effects of treatment on number of steps will be assessed using generalized estimating equations (GEE) with an unstructured variance-covariance matrix for measures on the same day. This model accounts for possible autocorrelation and linear trends between steps across time.

Data from the four small sample preliminary phases will be considered as descriptive data/information and will not be statistically analyzed.

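### Aim 3 has no stated method for individual heterogeneity: one unreplicated 2-week block per BCT, a population-averaged GEE and a report of observed data cannot separate response from chance or from the particular fortnight.

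*Combined protocol and SAP*

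**What the plan says.** Section 4 sets the aim: "Examine the novel individual-level heterogeneity of treatment effect made possible by the crossover, personalized trial design". The same aim goes on to pool results across participants and estimate the efficacy of "the four behavioral change techniques in increasing low-intensity walking by 2,000 steps, 5 days per week".

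The design gives each technique to each person once. Section 8 describes a 2-week baseline "followed by 8 weeks of monitoring their walking in response to each of the four behavioral change techniques (2 weeks per technique"), and section 11 (Intervention Delivery) has a randomized crossover "with each BCT delivered individually in one of four 2-week blocks".

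On analysis, section 12 makes one statement about heterogeneity: "Data will be reported transparently so that individual level heterogeneity can be assessed". It then plans a column graph of means and SDs, and one model: "The effects of treatment on number of steps will be assessed using generalized estimating equations (GEE"), said to allow for autocorrelation and linear trend. It names no participant-specific effect, variance component, interval or responder rule.

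Participants receive "a summary of their observed data to help them learn more about their responses to the four behavioral change techniques" (section 2). Section 11 calls this an "individual report that demonstrates their walking responses in relation to their assigned BCTs", and section 9 presents it as the person's responsiveness to each BCT. Section 14 says an outside company will help analyse the individual reports, but does not give its method. Section 10 does not list heterogeneity as an endpoint.

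**The concern.** A crossover supports statements about individual response when it can tell a person's reaction to a treatment from that person's ordinary variation between periods. That normally requires each treatment to be repeated within the person. Here nothing is repeated, so within one participant the technique and the fortnight in which it was given cannot be told apart. The 14 daily counts replicate days inside a block. They do not replicate the block.

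The stated model does not fill the gap. A GEE describes the average response across participants. Its working correlation is not an estimate of how much individuals differ in response, and it yields no effect for a given person. What remains is display of the observed block means. Those means will differ within every participant even if the four techniques are equivalent.

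Two things are at stake. Aim 3 could be reported from raw spread that chance also produces. And participants could read that spread as their own responsiveness, which is how section 9 describes it.

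**Working it through.** The plan states no figure to reproduce: section 12 justifies 60 participants by feasibility, with no SD, effect size or power.

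**Inputs.** From the documents: four BCT blocks and one baseline block of 14 days each, up to 60 participants, a 2,000-step target. Assumed, because the documents do not give them: daily within-person SD of 1,000 / 2,000 / 3,000 / 4,000 steps, lag-1 correlation of 0 or 0.2, and person-specific fortnight shifts with SD of 0, 500 or 1,000 steps. All chance figures take the techniques as identical.

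**1. What the design can separate.** There are 60 × 4 = 240 BCT block means. Removing 1 for the mean, 59 for participants, 3 for periods and 3 for BCTs leaves 240 − 1 − 59 − 3 − 3 = 174 degrees of freedom. Participant-by-BCT response and participant-by-fortnight variation share all 174.

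**2. Noise in a block mean.** With independent days, SE = SD/√14 = 267 / 535 / 802 / 1,069 steps.

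**3. Chance gap between best and worst block.** The expected range of four independent normal values is 2.059 SE, that is 2.059/√14 = 0.55 daily SD: 550 / 1,100 / 1,651 / 2,201 steps. With lag-1 correlation 0.2 the SE becomes 322 / 645 / 967 / 1,290 and the gap 664 / 1,328 / 1,991 / 2,655.

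**4. Chance of one BCT appearing to meet the target.** The SE of one block mean minus baseline is SD × √(2/14) = 378 / 756 / 1,134 / 1,512. Dividing 2,000 by these gives z = 5.29 / 2.65 / 1.76 / 1.32, so the chance of an apparent gain above 2,000 steps is about 0% / 0.4% / 4% / 9%.

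**5. Would a mixed model resolve it?** Only in part. In simulated trials with 60 people, SD 3,000 and lag-1 correlation 0.2, a mixed model with participant-by-BCT effects was fitted to the four BCT blocks. True heterogeneity of SD 500 with no fortnight shift gave a mean estimate of 485 steps. No heterogeneity with fortnight shifts of SD 500 gave 472. The data barely distinguish the two.

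**6. What that variance misses.** If a person responds equally to all four techniques, all four block means move together and the random intercept absorbs the move. With a common response of SD 1,000 steps and no BCT-specific differences, a moment estimate of the participant-by-BCT SD came out at 28 steps. So this variance says nothing about heterogeneity of gain over baseline.

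**7. What honest person-level intervals look like.** Using one person's own four blocks (4 × 13 = 52 error df), the Tukey half-width for any of the six BCT differences is 3.75 × SE (3.75 is the 95% studentized range point for 4 means), or about 1,000 / 2,010 / 3,010 / 4,010 steps with independent days. These intervals do not cover fortnight shifts. Treating the SE as known (critical point 3.63), at lag-1 correlation 0.2, SD 3,000 and shift SD 500, the block-mean SD is √(967² + 500²) = 1,089. A false contrast then needs a standardized range above 3.63 × 967/1,089 = 3.22, which occurs in about 10% of people instead of 5%. At SD 1,000 with the same shift, the threshold is 3.63 × 322/595 = 1.97, exceeded in about 50%.

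**The case against.** The other side has a good case. This is a feasibility pilot, and section 10 makes acceptability, scalability and satisfaction primary. Aim 3 promises to examine heterogeneity and keeps the language of estimation for pooled efficacy, so transparent display may be all that was meant. Section 14 treats the feasibility of modelling precise therapy as itself a question for the pooled results. The outside company may already use a sound per-person method, and the report template is not in the document. All step figures rest on assumed SDs.

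This limits the weight of the point but does not remove it. Displaying block means, however openly, does not separate response from noise, and calling them responsiveness invites that reading.

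Three stronger readings are tempting and not supported.

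- A reader might infer that participants will be misled. The documents do not say whether the reports carry uncertainty, so this is a possibility only.
- A reader might take each person's best technique and compare it with baseline, where chance exceeds 2,000 steps in about 0% / 1% / 12% / 24% of people. The plan speaks of responses to each of the four techniques and nowhere says that a best one will be picked, so the single-BCT figures apply.
- A reader might treat a participant-by-BCT variance as an upper bound on all heterogeneity. Step 6 shows that this is false for gain over baseline.

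**Conclusion.** The point holds as a gap in the analysis of one aim and in the basis of the participant reports. Followed as written, the plan would take observed block differences as evidence on individual heterogeneity, although identical techniques produce gaps averaging about 0.55 daily SD. How serious that is depends on the unknown daily SD: at 1,000 or 2,000 steps a single technique almost never mimics the 2,000-step target by chance, while at 3,000 or 4,000 it does so in about 4% or 9% of people. Autocorrelation and fortnight shifts would raise these figures, by amounts the documents do not allow one to fix. The pooled GEE comparison is not challenged here, and the primary feasibility objective is unaffected. The change should be made, but it does not stand in the way of the trial.

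**What to change.** In section 12, keep the GEE and add an exploratory linear mixed model of daily steps in the four BCT blocks, with a participant random intercept, random participant-by-BCT effects, BCT and period as factors, and autocorrelated daily errors. Report the participant-by-BCT variance with its interval, labelled as differences between BCTs within a person plus participant-by-fortnight variation. State that it is an upper bound only on heterogeneity between BCTs. Keep heterogeneity of gain over baseline descriptive, because baseline is always the first fortnight.

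In each participant report, show the observed block means with person-level intervals that allow for autocorrelation and for the six BCT comparisons. Say plainly that differences may reflect chance or the particular fortnight. Compute these from the person's own data: section 9 sends the report with the satisfaction survey when each person finishes, and estimates that borrow from other participants would have to wait for them. Use partially pooled person estimates in the end-of-study analysis only. State in section 14 that the outside company follows this method.

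The cost is modest extra analysis and template work, with no new data and no change in timing. Intervals will be wide and reports less striking. Fortnight confounding is disclosed, not removed: step 7 shows that false contrasts can stay common when fortnight shifts are large relative to daily noise, which is why the caveat is needed.
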